### 7.5.3 *Plasma hsTnI concentrations over 1 year.*

This will be done in three groups: patients with coronary 18F-fluoride uptake, patients without, and in all patients. We will calculate the area under the curve of the plasma hsTnI measurements from 30 days to 1 year, using nominal time points (30 days, 3 months, 6 months, 9 months, 1 year; not visit numbers) rather than actual dates. A value of 0.5ng/l will be used for troponin values below the limit of detection. Where there are missing values between two others, it will be assumed that the missing value lies on the straight line between the measured values either side. Where there are missing values

at the right hand end, the patient will be excluded. This will be modelled in a linear regression model, adjusted for age, sex and log baseline troponin. Unadjusted analyses (still adjusted for log baseline troponin) will also be presented. The difference in means between the treatment groups will be presented, along with a 95% confidence interval and p-value. Descriptive statistics will be presented for the area under the curve.

A term for coronary 18F-fluoride uptake (Y/N) will be added into the model for all patients, and the p-value for the interaction between coronary 18F-fluoride uptake and the treatment effect will be presented.

#### *7.5.4 Calcium score at 1 year.*

This will be done using 4 separate analyses. The method of measurement will be mass.

Plaque calcium score at 1 year at the site of baseline coronary 18F-fluoride uptake in patients with coronary 18F-fluoride uptake will be modelled in a linear regression model, adjusted for age, sex, log baseline troponin I and baseline plaque calcium score. Unadjusted analyses (still adjusted for baseline plaque calcium score) will also be presented. The difference in means between the treatment groups will be presented, along with a 95% confidence interval and p-value. Descriptive statistics will be presented for baseline, 1 year and the change between baseline and 1 year. Numbers with missing data values at baseline and 1 year will be reported, and descriptive statistics will be presented for the group with no missing data at either time point.

Plaque calcium score at 1 year at the site of referent plaque (a plaque with no baseline coronary 18F-fluoride uptake) in patients with coronary 18F-fluoride uptake will be modelled in a linear regression model, adjusted for age, sex, log baseline troponin I and baseline plaque calcium score. Unadjusted analyses (still adjusted for baseline plaque calcium score) will also be presented. The difference in means between the treatment groups will be presented, along with a 95% confidence interval and p-value. Descriptive statistics will be presented for baseline, 1 year and the change between baseline and 1 year. Numbers with missing data values at baseline and 1 year will be reported, and descriptive statistics will be presented for the group with no missing data at either time point.

Total calcium score at 1 year in patients with 18F-fluoride uptake will be modelled in a linear regression model, adjusted for age, sex, log baseline troponin I and baseline total calcium score. Unadjusted analyses (still adjusted for baseline total calcium score) will also be presented. The difference in means between the treatment groups will be presented, along with a 95% confidence interval and p-value. Descriptive statistics will be presented for baseline, 1 year and the change between baseline and 1 year. Numbers with missing data values at baseline and 1 year will be reported, and descriptive statistics will be presented for the group with no missing data at either time point.

Total calcium score at 1 year in patients without 18F-fluoride uptake will be modelled in a linear regression model, adjusted for age, sex, log baseline troponin I and baseline total calcium score. Unadjusted analyses (still adjusted for baseline total calcium score) will also be presented. The difference in means between the treatment groups will be presented, along with a 95% confidence interval and p-value. Descriptive statistics will be presented for baseline, 1 year and the change between baseline and 1 year. Numbers with missing data values at baseline and 1 year will be reported, and descriptive statistics will be presented for the group with no missing data at either time point.

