1.3 RATIONALE FOR STUDY

The rationale for this study is based on two main observations relevant to the pathogenesis of coronary artery disease.

1. The majority of episodes of plaque rupture are subclinical because thrombus formation is non-occlusive and microembolism causes covert myocardial micro-injury that is insufficient to cause overt symptoms.
2. Cycles of rupture and non-occlusive thrombus formation lead to plaque expansion and coronary artery disease progression.

These two features can now be tracked using a high-sensitivity cardiac troponin I assay and computer tomography coronary angiography respectively.

Given this central role of thrombosis in atherogenesis, anti-thrombotic interventions have major potential to impact on the consequences and progression of atherosclerotic disease [Williams *et al*, 1997; Rioufol *et al*, 2004; Kwon *et al*, 2005]. With the advent of more potent platelet inhibition with ticagrelor, there is now the opportunity to assess whether dual anti-platelet therapy can improve markers of myocardial injury and disease progression.

To enhance the opportunity to detect such effects, we propose a stratified medicine approach where we will specifically select patients who have evidence of high-risk or subclinical ruptured coronary artery plaque identified by coronary 18F-fluoride uptake. We will then compare outcomes between those with and those without uptake, anticipating that only patients with high-risk plaque will demonstrate evidence of reduced injury and disease progression.

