3 STUDY DESIGN

3.1 RATIONALE FOR STUDY DESIGN, DOSES AND CONTROL GROUPS

The study will be a randomised double blind placebo-controlled trial to ensure a rigorous study design and the avoidance of systematic biases of outcome measures. All recruited patients will undergo computed tomography coronary angiography and 18F-fluoride positron emission tomography (PET) scanning at baseline. Patients will then be randomised to ticagrelor 90 mg or matched placebo twice daily [Wallentin *et al*, 2009]. The dose has been selected on the basis of the PLATO trial [Wallentin *et al*, 2009]. The control groups will be two-fold. First there will be the active and inactive comparators of ticagrelor and placebo. Second we will examine for the presence and magnitude of an effect in the groups of patients with or without coronary 18F-fluoride uptake.

The primary outcome will be the comparison between ticagrelor and matched placebo on the change in plasma troponin concentration from baseline to one month in patients with coronary 18F-fluoride uptake. Secondary analyses will undertake the same assessment in patients without coronary 18F-fluoride uptake to determine whether this is particular to patients with high-risk coronary plaque or is seen in all patients with multivessel coronary artery disease.

Further longitudinal comparisons of these groups will determine whether the dominant effect on plasma troponin concentrations is seen only in the early phase or whether potential benefits are seen throughout the study period. Finally, we will assess whether in comparison to placebo, ticagrelor will inhibit progression of coronary atheroma (calcium score and plaque volume) at the site of high-risk coronary plaque.

An additional exploratory component to the study will be to assess the reproducibility and natural history of 18F-fluoride uptake within coronary plaques. This will be investigated with repeat PET scanning within a subgroup of the total population.

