### 7.5.2 *High sensitivity cardiac troponin I (hsTnI) concentration at 30 days in total study population.*

As Troponin I at 30 days is skewed, it will be log transformed prior to analysis. A value of 0.5ng/l will be used for values below the limit of detection. When reporting summary statistics and results of analyses, the logged and unlogged results will be reported, i.e. if we report a mean of the logged values, we will back-transform this mean to the original unlogged scale for ease of interpretation.

Troponin I, in all patients, will be modelled in a linear regression model, adjusting for age, sex, and log baseline troponin I. Unadjusted analyses (still adjusted for log baseline troponin) will also be presented. The difference in means between the treatment groups will be presented, along with a 95% confidence interval and p-value. Descriptive statistics will be presented for baseline, 30 days and the change between baseline and 30 days. Numbers with missing data values at baseline and 30 days will be reported, and descriptive statistics will be presented for the group with no missing data at either time point.

A term for coronary 18F-fluoride uptake (Y/N) will be added into the model for all patients, and the p-value for the interaction between coronary 18F-fluoride uptake and the treatment effect will be presented.

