#### *7.5.5 Plaque volume at 1 year*

Plaque volume ( $\text{mm}^3$ ) as originally intended is not available. Instead, we will use plaque calcium volume ( $\text{mm}^3$ ). This will be strongly correlated with plaque calcium mass which is being used as the plaque calcium score.

This will be assessed using 2 separate analyses.

Plaque volume at 1 year at the site of baseline coronary 18F-fluoride uptake, in patients with coronary 18F-fluoride uptake in patients with coronary 18F-fluoride uptake, will be modelled in a linear regression model, adjusted for age, sex, log baseline troponin I and baseline plaque volume. Unadjusted analyses (still adjusted for baseline plaque volume) will also be presented. The difference in means between the treatment groups will be presented, along with a 95% confidence interval and p-value. Descriptive statistics will be presented for baseline, 1 year and the change between baseline and 1 year. Numbers with missing data values at baseline and 1 year will be reported, and descriptive statistics will be presented for the group with no missing data at either time point.

Plaque volume at 1 year at the site of referent plaque (a plaque with no baseline coronary 18F-fluoride uptake) in patients with coronary 18F-fluoride uptake will be modelled in a linear regression model, adjusted for age, sex, log baseline troponin I and baseline plaque volume. Unadjusted analyses (still adjusted for baseline plaque volume) will also be presented. The difference in means between the treatment groups will be presented, along with a 95% confidence interval and p-value. Descriptive statistics will be presented for baseline, 1 year and the change between baseline and 1 year. Numbers with missing data values at baseline and 1 year will be reported, and descriptive statistics will be presented for the group with no missing data at either time point.

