#### **7.7 Subgroup analyses**

There are no planned subgroup analyses, other than those specified elsewhere in this Statistical Analysis Plan.

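### For the secondary CT progression outcomes, the SAP plans no test of whether the ticagrelor effect differs by uptake status or by plaque site, although it plans one for troponin

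*SAP*

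**What the plan says.** Protocol 1.3 states that outcomes will be compared between patients with and without uptake, "anticipating that only patients with high-risk plaque will demonstrate evidence of reduced injury and disease progression". Protocol 3.1 makes uptake status the second of its two control comparisons. It frames the CT aim more narrowly, as whether "ticagrelor will inhibit progression of coronary atheroma (calcium score and plaque volume) at the site of high-risk coronary plaque".

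For 30-day troponin, SAP 7.5.2 fits an all-patient model and says "the p-value for the interaction between coronary 18F-fluoride uptake and the treatment effect will be presented". SAP 7.5.3 does the same for the 1-year area under the curve.

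The CT outcomes are handled differently. For calcium score, SAP 7.5.4 says "This will be done using 4 separate analyses":

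- plaque calcium at the uptake site, in PET-positive patients;
- plaque calcium at a referent plaque without uptake, in PET-positive patients;
- total calcium in PET-positive patients;
- total calcium in PET-negative patients: "Total calcium score at 1 year in patients without 18F-fluoride uptake will be modelled in a linear regression model".

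For plaque volume, now measured as plaque calcium volume, SAP 7.5.5 says "This will be assessed using 2 separate analyses". These cover the uptake site and the referent plaque, both in PET-positive patients. Each of the six models yields its own treatment difference, 95% CI and p-value. SAP 7.7 closes the list: "There are no planned subgroup analyses, other than those specified elsewhere in this Statistical Analysis Plan".

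**The concern.** The expectation in Protocol 1.3 concerns a difference between treatment effects, and it covers disease progression as well as injury. The SAP supplies the matching test for injury and not for progression, and gives no reason.

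Protocol 9.2.2 asks only for the uptake site. The SAP adds the referent plaque and total calcium in PET-negative patients, which are of interest mainly as comparators, but no model makes the comparison. A reader then has separate p-values side by side and may take significance in one and not in the other as evidence that the effect is specific. That pattern does not test a difference.

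The missing term is not the same throughout. For total calcium it is treatment-by-uptake across all patients. For plaque calcium and plaque calcium volume it is treatment-by-site within PET-positive patients, where the two sites are paired.

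**Working it through.** **Inputs.** Protocol 9.1 gives 55 PET-positive patients per arm, 60% with uptake, 183 evaluable and 220 recruited. SAP 3 gives 1:1 allocation, and SAP 6 gives a two-sided 5% level. The documents give no SD for any CT outcome and no between-site correlation. Results are therefore in SD units, with equal SDs assumed across groups and a range of assumed correlations.

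**The plan's own figures.** The plan gives no figure for a CT comparison. Its sample size reproduces: a difference of 7.89 − 3.95 = 3.94 ng/L with SDs 9.34 and 1.89 gives 80.2% power at 48 per arm (unequal-variance t). After the allowance to 55 per arm, 2 × 55 / 0.60 = 183.3, matching 183.

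**Group sizes per arm.** Evaluable: 55 PET-positive and (183 − 110)/2 = 36.5 PET-negative. All recruited: 220 × 0.60/2 = 66 and 220 × 0.40/2 = 44.

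**1. Total calcium: false split when the true effects are equal.** The standardised effect in a group of n per arm is D/√(2/n). At 80% power in PET-positive it is 1.960 + 0.842 = 2.802. The same D gives 2.802 × √(36.5/55) = 2.28 in PET-negative, so power there is Φ(2.28 − 1.96) ≈ 63%. The groups are independent, so the chance that PET-positive is significant and PET-negative is not is 0.80 × (1 − 0.63) ≈ 30%.

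| Power in PET-positive | Positive significant, negative not |
|---|---|
| 50% | 32% |
| 80% | 30% |
| 90% | 22% |

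The rounded figures are the same for 66/44 and 55/36.5 per arm. With equal group sizes they would be p(1 − p): 25%, 16% and 9%. Unequal size is therefore only part of the cause.

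**2. Uptake site versus referent plaque.** Two correlated normal test statistics were simulated, with equal true effects and 80% power at each site. The uptake site is significant and the referent site is not in 16%, 13%, 11% and 9% of trials at assumed correlations of 0, 0.3, 0.5 and 0.7.

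**3. Power of the missing total-calcium test.** The interaction SE is SD × √(2/n₊ + 2/n₋). Suppose a benefit of 0.535 SD (the effect with 80% power at 55 per arm) is confined to PET-positive patients.

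- 55/36.5: SE = 0.302 SD, ratio 0.535/0.302 = 1.77, power Φ(1.77 − 1.96) ≈ 43%.
- 66/44: SE = 0.275 SD, ratio 1.94, power ≈ 49%.

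The difference detectable with 80% power is 2.802 × 0.302 = 0.85 SD (0.77 SD at 66/44).

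**4. Precision of the paired site contrast.** The SE of the treatment-by-site term is SD × √(4(1 − r)/n). At n = 55 per arm the detectable difference is 0.76, 0.63, 0.53 and 0.41 SD for r = 0, 0.3, 0.5 and 0.7.

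**The case against.** The strongest reply is that the stated CT objective needs no interaction. Protocol 2.1.2(c), 3.1 and 9.2.2 all ask about the effect at the uptake site, and the first model in each of SAP 7.5.4 and 7.5.5 estimates it. Protocol 2.1.4 lists progression throughout the coronary circulation as exploratory. This stands for the objective. It does not remove the comparison promised in Protocol 1.3, and the SAP itself places total calcium among the secondary outcomes.

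A second reply is that every model reports a difference with a 95% CI. For total calcium the two groups are independent, so an approximate contrast follows from the two published intervals. That is right. For the two sites it does not work properly, because the between-site correlation is not reported. Assuming independence is conservative if the correlation is positive, but it inflates the SE by 1/√(1 − r), for example 1.41 times at r = 0.5.

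Some stronger readings are tempting, and the documents do not support them:

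- *The trial cannot test its hypothesis of specificity.* Troponin, the primary biomarker, has interaction tests at 30 days and over 1 year. Protocol 1.3 also states an expectation, not a claim.
- *All six models are split by uptake group.* Only total calcium is. The other four are in PET-positive patients only.
- *The investigators will judge specificity from discordant p-values.* Neither document says so. The 30% applies only if someone reads the results that way.
- *The paired contrast is the most precise analysis available.* Its SE is √(2(1 − r)) times that of the uptake-site effect alone, which is 18% larger at r = 0.3. Pairing helps only relative to treating the sites as independent.

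**Conclusion.** The point holds for the secondary CT progression outcomes only. SAP 7.5.4 and 7.5.5 contain no treatment-by-uptake or treatment-by-site term, while the SAP plans the uptake interaction for troponin. The primary analysis and the uptake-site CT objective are unaffected.

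The risk lies in interpretation. With equal true effects, reading separate p-values would suggest specificity in about 22% to 32% of trials for total calcium (PET-positive power 90% to 50%), and in about 9% to 16% for plaque site at 80% power. These figures rest on normal approximations, equal SDs and assumed correlations.

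The remedy has a real limit. With power of about 43% to 49% under the assumed 0.535 SD effect, a non-significant total-calcium interaction would not show equal effects. That is a reason to report the estimate with its interval. It is not a reason to leave the comparison to separate p-values. The change should be made, as a matter of moderate importance.

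**What to change.** Keep the six separate estimates and add to SAP 7.5.4 and 7.5.5:

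1. One all-patient model for total calcium score with treatment, uptake and treatment-by-uptake, adjusted for age, sex, log baseline troponin and baseline total calcium.
2. For plaque calcium score, and likewise for plaque calcium volume, one model in PET-positive patients that includes both sites, with a patient random effect, the site-specific baseline value, the SAP's usual covariates, and treatment, site and treatment-by-site terms.
3. Report each interaction estimate with its 95% CI, and base any statement that the CT effect is specific to high-risk plaque on these terms.
4. State in advance that interaction power is low, so a non-significant term is not evidence of equal effects.

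The cost is a paragraph in the SAP and three further SAS models on data already due to be collected. SAP 6 already provides for an updated SAP with reasons. The change should be made before the treatment results are seen, because the same tests added afterwards would be post hoc.

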#### *7.5.5 Plaque volume at 1 year*

Plaque volume ( $\text{mm}^3$ ) as originally intended is not available. Instead, we will use plaque calcium volume ( $\text{mm}^3$ ). This will be strongly correlated with plaque calcium mass which is being used as the plaque calcium score.

This will be assessed using 2 separate analyses.

Plaque volume at 1 year at the site of baseline coronary 18F-fluoride uptake, in patients with coronary 18F-fluoride uptake in patients with coronary 18F-fluoride uptake, will be modelled in a linear regression model, adjusted for age, sex, log baseline troponin I and baseline plaque volume. Unadjusted analyses (still adjusted for baseline plaque volume) will also be presented. The difference in means between the treatment groups will be presented, along with a 95% confidence interval and p-value. Descriptive statistics will be presented for baseline, 1 year and the change between baseline and 1 year. Numbers with missing data values at baseline and 1 year will be reported, and descriptive statistics will be presented for the group with no missing data at either time point.

Plaque volume at 1 year at the site of referent plaque (a plaque with no baseline coronary 18F-fluoride uptake) in patients with coronary 18F-fluoride uptake will be modelled in a linear regression model, adjusted for age, sex, log baseline troponin I and baseline plaque volume. Unadjusted analyses (still adjusted for baseline plaque volume) will also be presented. The difference in means between the treatment groups will be presented, along with a 95% confidence interval and p-value. Descriptive statistics will be presented for baseline, 1 year and the change between baseline and 1 year. Numbers with missing data values at baseline and 1 year will be reported, and descriptive statistics will be presented for the group with no missing data at either time point.

#### *7.5.6 Reproducibility of 18F-fluoride uptake detected on PET imaging at 1 week.*

Within the group entered into this sub-study, descriptive statistics will be presented. This will include the proportion of PET positive patients at 1 week, among those who were PET positive at baseline; and the proportion of PET negative patients at 1 week, among those who were PET negative at baseline. Crude overall agreement will be presented, along with a kappa statistic (with the understanding that the margins were fixed in the design of this study).

#### *7.5.7 Natural history of 18F-fluoride uptake over 1 year.*

Tables will be produced to summarise the groups of patients measured at baseline and 3 months, baseline and 6 months, and baseline and 1 year. Descriptive statistics will show the proportion of PET positive/negative patients at the later time point, among those who were PET positive at baseline; and the proportion of PET positive/negative patients at the later time point among those who were PET negative at baseline.

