2.1.2 Secondary Objectives

- a) To assess whether ticagrelor will reduce plasma high-sensitivity troponin concentrations in patients without increased coronary 18F-fluoride uptake.
- b) To assess whether ticagrelor will reduce plasma high-sensitivity troponin concentrations over a 1-year time frame.
- c) To assess whether ticagrelor will reduce coronary plaque volume or calcium score at the site of 18F-fluoride uptake.
- d) To confirm the reproducibility of 18F-fluoride PET positivity
- e) To assess the natural history of 18F-fluoride PET positive coronary plaque

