The positron emission tomography scans will be reconstructed in multiple phases of the cardiac cycle, with the diastolic phase (50-75%) used for analysis. The computed tomography coronary angiography scans will be reconstructed at 0.75 x 0.7 mm and 0.6 x 0.3 mm for retrospective and prospective acquisitions respectively at 60%, 65% and 70% of the cardiac cycle. Additional reconstructions will be undertaken as necessary. Positron emission tomography scans will correct for cardiac motion correction using electrocardiogram-gated images.

18F-F PET Natural History Sub-study

Using the same scan process as outlined above a sub-group of patients will be selected for 1 additional PET scan. In total this will involve 80 patients out of the total cohort. The first 20 participants to be scanned will be to assess the reproducibility of 18F-fluoride uptake and will undergo a second PET scan at the randomisation visit (1 week after the baseline scan). This group will comprise 10 patients from both of the PET positive and PET negative samples. Following this we will investigate the natural history of 18F-fluoride uptake by performing repeat PET scans on 60 patients in total from the initial PET positive sample with 20 patients scanned at the 3 month, 6 month and 12 month follow up visits. No individual patient will undergo more than 2 PET scans during the course of the study. In order to allow accurate co-registration of images, repeat CT coronary angiograms will be performed at the time of the repeat PET scans. The additional PET scan for those in the sub-study will be performed at the 1 week, 3 month, 6 month or 12 month visit but the additional CTCA scan will only be performed at 1 week, 3 month or 6 month visits as the CTCA scan at 12 months will be performed on all participants irrespective of whether they are taking part in the sub-study

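### SAP 7.5.7 tabulates repeat-PET status by patient only, while the natural-history objective is about plaques; a per-plaque table should be added beside it

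*SAP*

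**What the plan says.** The protocol names the plaque as the thing to be followed. Objective 2.1.2(e) reads "To assess the natural history of 18F-fluoride PET positive coronary plaque", and section 3.1 says the sub-study will "assess the reproducibility and natural history of 18F-fluoride uptake within coronary plaques". Section 7.2.4 adds the means of matching sites between scans: "In order to allow accurate co-registration of images, repeat CT coronary angiograms will be performed at the time of the repeat PET scans".

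On size, section 7.2.4 says "In total this will involve 80 patients out of the total cohort". Twenty are rescanned at about 1 week for reproducibility: "This group will comprise 10 patients from both of the PET positive and PET negative samples". The other 60 all come from the PET-positive sample, with 20 rescanned at each of 3, 6 and 12 months.

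The SAP then works by patient. For natural history (7.5.7): "Descriptive statistics will show the proportion of PET positive/negative patients at the later time point, among those who were PET positive at baseline". For reproducibility (7.5.6) it lists "the proportion of PET positive patients at 1 week, among those who were PET positive at baseline", the matching proportion for baseline-negative patients, crude agreement and kappa. Neither section specifies the status of individual plaques, a count of positive plaques or a quantitative uptake measure at the repeat scan. Elsewhere the SAP does work by site: 7.5.4 and 7.5.5 analyse calcium mass and calcium volume at the site of baseline uptake.

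**The concern.** A patient-level yes/no answers a plaque-level question exactly only when each patient has one positive plaque and no new uptake appears elsewhere. Otherwise two kinds of change disappear from the 7.5.7 table: a plaque that resolves while another in the same patient stays positive, and a plaque that becomes positive in a patient who already was. Both are part of the natural history of positive plaque.

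All 60 patients in this group are positive at baseline, so the baseline-negative row that 7.5.7 also plans would be empty for them. What remains is one proportion for each group of 20. A high proportion still positive could mean that individual plaques persist, or only that patients with several plaques rarely lose all of them. The SAP does not plan to report the number of positive plaques per patient, so a reader could not tell these apart.

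**Working it through.** **Plan's own figure.** Sub-study size: 10 + 10 + 3 × 20 = 80, as stated. No stated figure is wrong; the issue is the unit of analysis.

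**Inputs that are not in the documents.**
- *Rule for patient positivity.* Taken as any coronary uptake. This is inferred from the yes/no uptake variable used for minimisation (Protocol 5.6.1) and in the interaction model (SAP 7.5.2).
- *Positive plaques per patient, k.* Assumed to be 1, 2 or 3.
- *Probability that a positive plaque resolves by the later scan, r.* Assumed to be 20%, 30% or 50%.
- *Independence of plaques within a patient, and no new uptake.* Assumed.

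**Patients who turn negative.** All k plaques must resolve, so the probability is r^k. Each cell gives the percentage and the expected number in a group of 20.

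| r per plaque | k = 1 | k = 2 | k = 3 |
|---|---|---|---|
| 20% | 20% (4.0) | 4% (0.8) | 0.8% (0.16) |
| 30% | 30% (6.0) | 9% (1.8) | 2.7% (0.54) |
| 50% | 50% (10.0) | 25% (5.0) | 12.5% (2.5) |

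**A mixed group.** If half the patients have one positive plaque and half have two, with r = 30%: 0.5 × 0.30 + 0.5 × 0.09 = 19.5%, or 3.9 of 20.

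**Changes scored as no change, k = 2.** Exactly one of the two plaques resolves with probability 2r(1 − r): 32%, 42% and 50% of patients for r = 20%, 30% and 50%.

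**Where the gap closes.** At k = 1 with no new uptake, patient-level and plaque-level rates are identical. If plaques within a patient tend to resolve together, the gap narrows, and it vanishes if they always do. New uptake elsewhere widens it.

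**Reproducibility at 1 week.** The direction is not the same in the two halves of the 20. Among the 10 baseline-positive patients, two scans positive at different plaques count as agreement, so patient scoring can be more lenient than plaque scoring. Among the 10 baseline-negative patients it is stricter. If 5% of negative plaques lit up falsely on rescan and a patient had 4 (both assumed), the patient would stay negative with probability 0.95^4 = 81%, against 95% per plaque.

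**The case against.** The strongest reply concerns reproducibility, and it stands. Objective 2.1.2(d) reads "To confirm the reproducibility of 18F-fluoride PET positivity" and names no plaque; only the looser wording of Protocol 3.1 does. Patient-level status defines the primary population, is a minimisation factor and is the interaction term. Whether a patient is classified the same way a week later is therefore what the primary analysis depends on. The list in SAP 7.5.6 is also worded as non-exhaustive. A reader might infer that patient scoring always overstates reproducibility, or that the patient-level tables should be demoted. The calculation for negative patients rules out the first, and objective (d) does not support the second.

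The second reply is that the size is unknown. This also stands. The protocol's statement that plaque events are commonly multiple (section 1.1.1) refers to acute coronary syndromes and fatal disease, and section 4.3 excludes an acute coronary syndrome in the previous 12 months. The multivessel criterion in section 4.2 concerns stenosis or previous revascularisation, not sites of uptake.

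A reader might also infer that the radiation from the additional angiogram buys data that go unused. The documents do not support that. The stated purpose is co-registration, and deciding whether a patient has coronary uptake may itself need the coronary anatomy.

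Finally, it could be said that the sub-study is exploratory, as Protocol 3.1 calls it, and so falls under SAP 7.8, which leaves exploratory objectives out of the main report. That does not close the gap. Protocol 2.2.2(f) and (g) list both items as secondary endpoints, the SAP analyses them as such, and the exploratory objectives in Protocol 2.1.4 describe no plaque-level analysis of the repeat PET scans.

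**Conclusion.** The mismatch of unit in SAP 7.5.7 is real: the objective is about plaques and the only planned table is about patients. Under the inferred any-uptake rule, the table shows only complete loss of uptake in patients with several positive plaques, and it misses new uptake in patients who are already positive. With 30% independent resolution per plaque, the patient-level rate would be 30%, 9% or 2.7% for one, two or three positive plaques. That is an illustration rather than an estimate, because neither the number of plaques nor the resolution rate is given.

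It would go too far to say that the planned table cannot answer objective (e) at all. It is fully informative for patients with a single positive plaque and no new uptake, and for the others it still reports complete loss of uptake. The analysis is descriptive, makes no treatment comparison and does not touch the primary endpoint. This is a worthwhile, inexpensive improvement and not a threat to the trial.

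**What to change.** In SAP 7.5.7, keep the patient-level table and add a per-plaque table read from the co-registered images. It should show:

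- for each baseline-positive plaque, whether it is persistent or resolved at the later scan;
- any site of new uptake;
- the number of positive plaques per patient at each scan;
- proportions with confidence intervals that allow for clustering of plaques within patient.

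State in the SAP the rule that makes a patient PET positive and the rule for matching a plaque between scans.

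In SAP 7.5.6, keep patient-level agreement and kappa as the main result. Same-site agreement among the 10 baseline-positive patients may be added as a supplementary line.

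The cost is SAP wording, plaque-matching definitions and some extra reading of images already acquired, in at most 60 patients for 7.5.7 and 10 for the optional line. Baseline uptake sites already have to be located for 7.5.4, and no scan or visit is added. With 20 patients per time point the intervals will be wide, and the report should say so.
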